9.4 Genetics OR Pharmacogenomics

Genetics are not evaluated in this study.

9.5 Biomarkers

Biomarkers are not evaluated in this study.

9.6 Immunogenicity Assessment

Not applicable.

9.7 Health Economics OR Medical Resource Utilisation and Health Economics

Health economics OR medical resource utilisation and health economics parameters are not evaluated in this study.

10 STATISTICAL CONSIDERATIONS

The Statistical Analysis Plan will be finalised prior to database lock. It will include a more technical and detailed description of the statistical analyses described in this section.

10.1 Sample Size Determination

No formal sample size calculation was performed. It is estimated that at least 8 subjects per age range will enable estimation of rezafungin PK in subjects from birth to <18 years of age.

10.2 Statistical Hypotheses

No statistical hypotheses are planned for the study.

10.3 Analysis Sets

The following populations will be used

Table 4 Definition of Analysis Populations

Populations Analysis Set	Description
Enrolled set	All subjects who sign the ICF
Safety analysis set	All subjects who receive any amount of the rezafungin infusion
PK analysis set	All subjects who receive the single IV infusion of rezafungin and provide at least one blood sample for measurement of rezafungin plasma concentration

ICF=Informed Consent Form; IV=intravenous; PK=pharmacokinetic

10.4 Statistical Analyses

10.4.1 General Considerations

In general, continuous data will be summarised by group using descriptive statistics. Categorical data will be summarised by group as the number and percentage of subjects in each category.

Baseline is defined as the last value prior to IV infusion of rezafungin (Screening).

10.4.2 Demographic and Baseline Characteristics

Demographics (including age [chronological age], sex, and race) and baseline characteristics (including height, weight, and disease characteristics) will be presented descriptively, overall and by group.

10.4.3 Primary Endpoints Analyses

For Parts 1 and 2, PK parameters are primary endpoints for this study. The following PK parameters will be determined: C_{max} , T_{max} , AUC_{0-t} , $AUC_{0-\infty}$, CL, V_{ss} , V_z , and $t_{1/2}$.

For Part 3, as only three plasma concentrations will be determined from each subject, there will not be sufficient data to determine PK parameters. Therefore, the plasma concentrations will be listed and summarised using descriptive statistics.

For details see Section [10.5](#).

10.4.4 Secondary Endpoints Analyses

Safety will be assessed through treatment-emergent AEs (TEAEs), SAEs, AESIs, clinical laboratory tests, vital signs, 12-lead ECGs, and physical examination.

The Safety Analysis Set will be used for the analysis of safety data.

10.4.5 Adverse Events

Adverse events will be coded using the most recent version of Medical Dictionary for Regulatory Activities (MedDRA) coding system to give a SOC and Preferred Term (PT) for each AE.

A treatment-emergent AE (TEAE) is defined as any event not present prior to the administration of the IP infusion or any event already present that worsens in either severity or frequency following exposure to the IP.

Only treatment-emergent AEs will be summarised.

The number and percentage of subjects experiencing TEAEs will be summarised by group, severity, and relation to IP. TEAEs will be summarised by MedDRA SOC and PT. All AEs will be listed by subject. The number and percentage of subjects reporting at least one TEAE will be summarised by PT nested within SOC for each group (Groups 1, 2, 3, and 4), and overall, for each of the following AE types:

- Any TEAE
- Any related TEAE
- Any severe TEAE
- Any related severe TEAE
- Any SAE
- Any related SAE
- Any SAE leading to death
- Any AE leading to discontinuation
- Any AE requiring additional therapy

The number and percentage of subjects with any AE will be summarised by the DAIDS grades as follows:

- Mild (Grade 1): Mild symptoms causing no or minimal interference with usual social & functional activities with intervention not indicated
- Moderate (Grade 2): Moderate symptoms causing greater than minimal interference with usual social & functional activities with intervention indicated
- Severe (Grade 3): Severe symptoms causing inability to perform usual social & functional activities with intervention or hospitalization indicated
- Life-threatening (Grade 4): Potentially life-threatening symptoms causing inability to perform basic self-care functions with intervention indicated to prevent permanent impairment, persistent disability, or death
- Death (Grade 5): all deaths related to an AE

10.4.6 Laboratory Values

All laboratory data will be converted to International System of Units for reporting and processing purposes.

Clinical laboratory data to be summarised include haematology, blood chemistry, and urinalysis. The clinical laboratory parameters to be assessed are listed in [Appendix 2](#).

Clinical laboratory parameters at each timepoint and change from baseline to each post-baseline timepoint will be summarised using descriptive summary statistics for each parameter by group. Clinical laboratory values for each parameter will be assigned an LNH classification according to whether the value is lower (L), within (N) or higher (H) than the reference range for that parameter. The values will be summarised using shift tables from baseline to worst on study result with respect to reference range values (low, normal, high) for each parameter by group. Clinical significance of the laboratory value change will be stated.

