The Safety Analysis Set (i.e., all subjects who have received any amount of rezafungin) will be used for the analysis of safety data.

Safety will be evaluated through treatment-emergent adverse events (TEAEs), serious adverse events (SAEs), adverse events of special interest (AESIs), clinical laboratory, vital signs, electrocardiogram (ECG), and physical examination findings. TEAEs are defined as adverse events (AEs) with an onset on or after administration of the investigational product (IP; rezafungin) until the Follow-up.

Adverse events will be coded using the most recent version of the Medical Dictionary for Regulatory Activities (MedDRA).

The number and percentage of subjects experiencing TEAEs will be summarised by group, severity, and relation to IP. Treatment-emergent adverse events will be summarised by MedDRA System Organ Class and Preferred Term. The number and percentage of subjects reporting at least one TEAE will be summarised for each group (Groups 1, 2, 3, and 4), and overall. All AEs will be listed by subject.

Clinical laboratory data to be summarised include haematology, blood chemistry, and urinalysis. Laboratory data will be converted to International System of Units for reporting and processing purposes. Absolute values and changes from baseline will be presented descriptively. Laboratory data outside the reference ranges will be flagged, and clinical significance of the laboratory value change will be stated. Vital signs and 12-lead ECG data will be summarised by group and listed by subject. The number and percentage of subjects with clinically significant ECG findings will be summarised by group for each time-point. A summary of abnormal physical examination findings by group and scheduled visit (Study day) will be presented.

Interim Analysis

No formal interim analysis is planned for this study.

[figure not shown]
A DSMB has been appointed for this study to monitor the safety. Three interim reviews by the DSMB are planned during the study: The first interim review will be performed after completion of Part 1 (Group 1). The enrolment for Part 2 (Group 2 and Group 3) will commence only after DSMB review of Group 1 data and a decision to go ahead.

A second interim review by the DSMB is planned when data from 50% of the subjects enrolled in Part 2 are available.

[figure not shown]

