Analysis of the safety data obtained in ReSTORE indicates that rates of TEAEs and SAEs were comparable between the rezafungin and caspofungin arms. There were no apparent imbalances between the treatment groups in System Organ Classes (SOCs) of AEs. Related SAEs were similar in number between the two groups. There were no laboratory abnormalities that were commonly associated with either study drug, though there were some imbalances in

the 2-grade increases in toxicity for liver function tests that favours rezafungin. Furthermore, there were no apparent differences noted between vital sign and ECG data among the treatment groups.

Two specific types of AEs were found to be associated with rezafungin in clinical trials: infusion-related reactions and phototoxicity. In ReSTORE, there were 2 cases of infusion intolerance associated with rezafungin dosing and one in the caspofungin arm. While an AE of sunburn was observed in one subject in the Phase 2 STRIVE study following prolonged exposure to the sun, no phototoxicity occurred in the ReSTORE study.¹

Due to the findings of tremors in monkeys exposed to prolonged, high doses (9.2X the exposure to the proposed commercial dose in adults), close attention was paid to any neurologic AEs (i.e., ataxia, neuropathy, and tremor). These neurologic AEs were balanced between the rezafungin and caspofungin study groups, with 2 subjects having tremors in the rezafungin group (0 in the caspofungin group) and 2 subjects having neuropathy in the caspofungin group (0 in the rezafungin group). These 2 cases of tremors were mild in severity and reversible.

More detailed information about the known and expected benefits and risks and reasonably expected AEs of rezafungin (based on the adult clinical trials) can be found in the IB.

Summary of Benefit and Risk Evaluation

As this is a single-dose study, there is no direct clinical benefit expected for the subjects who will participate in this study. The information obtained from this study will be used for the further clinical development of rezafungin in the paediatric population.

The risk of AEs is minimised by careful selection of doses and participants for the study, the relatively short duration (single dose) of IP exposure, lowered infusion rate, and the extent of safety monitoring incorporated into the study.

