6.2 Exclusion Criteria

Subjects are excluded from the study if any of the following criteria apply.

1. History of anaphylaxis, hypersensitivity, or any serious reaction to the echinocandin class of antifungals and/or excipients of this formulation, including, but not limited to, hereditary sugar disorders (e.g., fructose intolerance, sucrase-isomaltase deficiency), or echinocandin-induced exfoliative skin disorders (e.g., Stevens-Johnson syndrome or toxic epidermal necrolysis)

2. Subject has a concurrent medical condition that in the opinion of the Investigator and/or medical monitor precludes enrolment into the study
3. Evidence of impaired hepatic or renal functions, as defined by aspartate aminotransferase (AST) or alanine aminotransferase (ALT) >3 times the upper limit of normal (ULN), conjugated bilirubin >24 µmol/L (1.4 mg/dL), serum creatinine >177 µmol/L (2 mg/dL), or receiving renal replacement therapy
4. The Investigator anticipates the subject becoming anaemic and not tolerating blood draws during the study period
5. Subjects have intestinal hypoxia, ischaemia, necrosis, or necrotising enterocolitis
6. Neonates with hyperbilirubinaemia and requiring phototherapy
7. History of severe ataxia, persistent tremors (e.g., due to persistent hypoglycaemia, persistent hypocalcaemia, encephalopathy, etc.), intracranial haemorrhage, or neuropathy, or a diagnosis of epilepsy, multiple sclerosis, or a movement disorder (including, but not limited to, cerebral palsy and muscular dystrophy), any of which is of Grade 2 or higher, based on the Division of Acquired Immunodeficiency Syndrome (DAIDS) criteria, Version 2.1
8. Planned or ongoing therapy at Screening or during the course of the study with a known severe neurotoxic medication (see [Appendix 4](#)) or CNS irradiation, or with a known moderate neurotoxic medication in a subject with ataxia, persistent tremors, intracranial haemorrhage, motor neuropathy, or sensory neuropathy, any of which is of Grade 1 or higher, based on the DAIDS criteria, Version 2.1 (see [Appendix 3](#))
 - a. Coadministration of vincristine (maximum: 2 mg/dose) with a dosing interval of every 21 days or less frequent is permitted in subjects without a history of ataxia, persistent tremors, intracranial haemorrhage, motor neuropathy, or sensory neuropathy **AND** not receiving concomitant azole therapy during the course of the study (from signing the informed consent to the follow-up visit on Day 30 ± 5).

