Appendix 9: Protocol Amendment History

Amendment 3 (18 Jul 2023)

Overall Rationale for the Amendment: This amendment is to clarify the neurotoxicity risk of vinca alkaloids (one of the prohibited neurotoxic concomitant medications).

Section # and Name	Description of Change	Brief Rationale
6.2 Exclusion Criteria; Appendix 4: List of Prohibited Concomitant Neurotoxic Medications	Addition of the dosing frequency of vinca alkaloids to define the risk level of neurotoxicity; addition of the maximum dose of vincristine	To clarify the neurotoxicity risk of vinca alkaloids

Amendment 2 (26 May 2023)

Overall Rationale for the Amendment: This amendment is to incorporate the updates requested by the European Medicines Agency (EMA) and UK Medicines and Healthcare products Regulatory Agency (MHRA) to have a global protocol and to update the safety reporting processes.

Section # and Name	Description of Change	Brief Rationale
Table 1: Schedule of Assessments for Part 1 and Part 2	Addition of vital sign assessments to all visits on Day 1; clarification of PK sampling procedure in withdrawn subjects in the footnote	To align with study procedure
6.2 Exclusion Criteria	Clarification of criterion #12	To clarify the criterion
6.2 Exclusion Criteria and 10.4.5 Adverse Events	Changed adverse event grading from CTCAE to DAIDS	The DAIDS grading system has age-specific definitions
3.3 Benefit and Risk Evaluation, 9.2.6 Adverse Event of Special Interest and Appendix 3 AEs and SAEs: Definition and Procedures for Recording, Evaluating, Follow-up, and Reporting	Updated safety reporting process to delete EDC and to change preferred method; specified the duration required for protection from phototoxicity	To align with the study's Safety Management Plan; to clarify the duration for phototoxicity

Section # and Name	Description of Change	Brief Rationale
Throughout	Editorial changes	Minor editorial changes associated with text added or removed based on the above changes and correcting typographical errors in referencing.

Amendment 1 (UK) (17 Apr 2023)

Overall Rationale for the Amendment: This amendment is based on requests from the Medicines & Healthcare products Regulatory Agency (MHRA).

This amendment is considered to be non-substantial based on the criteria set forth in the medicines for human use (clinical trials) regulation 2004 S.I. 2004/1031.

Section # and Name	Description of Change	Brief Rationale

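### The only categorical laboratory table, a low/normal/high shift, cannot show further worsening in a child already outside the range at baseline

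*Combined protocol and SAP*

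**What the plan says.** Protocol section 10.4.6 gives each laboratory value one of three classes. It is "assigned an LNH classification according to whether the value is lower (L), within (N) or higher (H) than the reference range for that parameter". The table built on this is described as follows: "The values will be summarised using shift tables from baseline to worst on study result with respect to reference range values (low, normal, high"). One such table is made per parameter within every age group.

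The same section also plans statistics on the values at each timepoint, and "change from baseline to each post-baseline timepoint will be summarised using descriptive summary statistics for each parameter by group". It adds: "Clinical significance of the laboratory value change will be stated". The synopsis says: "Laboratory data outside the reference ranges will be flagged, and clinical significance of the laboratory value change will be stated". No criteria for clinical significance are given. No table by toxicity grade or by multiple of ULN is planned for laboratory values.

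On who enters, criterion 3 of section 6.2 excludes "aspartate aminotransferase (AST) or alanine aminotransferase (ALT) >3 times the upper limit of normal (ULN"), so values between 1 and 3 x ULN are admitted. Section 6.2 sets no threshold for any blood count.

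On timing, Tables 1 and 2 (footnote g) schedule laboratory tests at Screening and at Follow-up (Day 30 ± 5) only. Sections 9 and 9.2.10 allow unscheduled and repeat tests.

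On grading, section 10.4.5 and Appendix 3 apply DAIDS v2.1 to adverse events. The reason given in Appendix 9 for moving to it is: "The DAIDS grading system has age-specific definitions".

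**The concern.** A three-class shift table records only whether a value crosses a reference limit. Once a child is beyond a limit at baseline, nothing further in that direction changes the cell. A child with raised transaminases whose values climb, or one with low neutrophils whose count falls further, is tabulated as unchanged.

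This study can be expected to enrol some such children. They are recruited as inpatients on systemic antifungals, and raised transaminases are admitted up to 3 x ULN.

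Clinical laboratory evaluation is a named component of the secondary safety endpoint (section 4). A reader who takes the shift table as the summary of laboratory worsening would be least well served for the children who start out abnormal.

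**Working it through.** The plan states no figure to reproduce here. The check applies the rule in 10.4.6 to illustrative values, then asks what each other planned summary would show.

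**1. The low/normal/high rule.** ALT is in multiples of ULN, so a value above 1 is high. The starting value of 2.9 lies within criterion 3; all values are illustrative.

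| Baseline | Worst | Ratio | Cell in planned table |
|---|---|---|---|
| 2.9 | 1.1 | 1.1/2.9 = 0.38 | high to high |
| 2.9 | 2.9 | 1.00 | high to high |
| 2.9 | 6 | 6/2.9 = 2.07 | high to high |
| 2.9 | 12 | 12/2.9 = 4.14 | high to high |
| 0.9 | 1.1 | 1.1/0.9 = 1.22 | normal to high |

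A partial improvement, no change and a fourfold rise share one cell. A trivial change across the limit counts as a shift.

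**2. Change from baseline.** Take a group of 8 in which seven do not change and one changes by d. The mean is d/8, the SD is d/√8, the median and upper quartile are 0, and the maximum is d.

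- 2.9 to 6: d = 3.1, mean 3.1/8 = 0.39, SD 1.10, maximum 3.1.
- 2.9 to 12: d = 9.1, mean 9.1/8 = 1.14, SD 3.22, maximum 9.1.

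The rise shows in the mean, the SD and, if reported, the maximum (10.4.6 does not list its statistics). It does not show in the median or quartiles, and it is not linked to baseline status. Two further limits apply:

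- Change is planned to each post-baseline timepoint, and only Day 30 ± 5 is scheduled. For vital signs, section 10.4.7 does plan change to the worst result; 10.4.6 does not. As written, an unscheduled peak in a laboratory value reaches only the table that cannot size it.
- Tests are run by local laboratories (Appendix 2) at about 10 sites in at least 3 countries (section 5.1). Values are converted to common units, but change is not expressed relative to each laboratory's own limit.

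**3. Flags.** A child who is high at both visits is flagged at both, whatever the size of the change.

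**4. Adverse events.** Appendix 3 counts a laboratory worsening as an adverse event if the investigator finds it clinically significant. Section 9.2.10 and Appendix 3 set aside abnormalities tied to the underlying disease unless they are judged worse than expected. That exception bears most on children who enter abnormal.

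**5. How many children.** The documents give no rate of out-of-range baselines. For an assumed rate p per parameter, with children independent, the expected number per group is 8p and the chance of at least one is 1 − (1 − p)^8.

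| Assumed p | Expected of 8 | P(at least one) |
|---|---|---|
| 10% | 0.8 | 0.57 |
| 25% | 2 | 0.90 |
| 50% | 4 | 0.996 |
| 75% | 6 | >0.999 |

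**6. With finer categories.** Using illustrative bands of >1–3, >3–5, >5–10 and >10 x ULN, 2.9 to 6 moves to >5–10 and 2.9 to 12 moves to >10. The stable child and the one falling to 1.1 both stay in >1–3. DAIDS laboratory cut-offs are not in the documents and were not used.

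**The case against.** The strongest reply is that the shift table does not stand alone. Change from baseline is summarised, out-of-range values are flagged, and clinical significance is stated. A worsening that the investigator judges clinically significant is an adverse event, and it is then graded by DAIDS, tabulated by grade and listed by subject. A large rise would escape that route only if the investigator judged it not clinically significant. This stands, and it means that a reader who infers that laboratory worsening would go wholly unseen goes too far. It narrows the gap but does not close it, for the reasons in steps 2 to 4 of the working.

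A reader might also infer that the plan contradicts its own choice of DAIDS. It does not. DAIDS was adopted for adverse events, and the Grade 4 stopping rule in section 8.1 counts related adverse events, not laboratory grades.

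A third tempting inference is that a graded table would allow comparison with the adult trial, where section 3.3 mentions "the 2-grade increases in toxicity for liver function tests that favours rezafungin". The scale used there is not named, so comparability is not shown.

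Two further points carry weight. With one scheduled post-dose sample, no choice of categories can recover a rise and fall between visits. And section 10 says that a more detailed analysis plan will be finalised before database lock. That plan could add these tables, but the low/normal/high table is the method now stated, so the addition should be asked for.

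**Conclusion.** The point holds as a minor one. The planned shift table cannot separate further worsening from stability or partial improvement in a child already beyond the same limit at baseline, and the remaining provisions cover this only in part.

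The loss of information follows from the rule itself and needs no assumption. How many children it affects does need one: 0.8 to 6 of 8 per group for assumed baseline rates of 10% to 75% per parameter. The documents do not support any particular rate, so a statement that most children would be affected is not warranted.

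Severity is minor because laboratory evaluation is one part of a descriptive secondary endpoint, no hypothesis is tested, and the primary pharmacokinetic analysis is untouched.

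**What to change.** In section 10.4.6 and the analysis plan, keep the low/normal/high table and add the following, using the worst post-baseline result with unscheduled results included:

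1. A shift from baseline to worst by DAIDS v2.1 grade for gradable parameters, with low and high directions tabulated separately where both are graded. This also settles what worst means for a parameter that can be abnormal either way.
2. A count of subjects whose grade rises by two or more.
3. Categories in multiples of each laboratory's own ULN, at baseline and worst, for ALT, AST and bilirubin.

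Do not present the two-grade count as comparable with the adult trial unless the grading scale is confirmed to be the same.

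The cost is analysis-plan text and some programming. No new samples are needed, because the values and reference ranges are already required for the planned table. The added tables will be sparse at 8 per group, and with one scheduled post-dose sample the gain will be modest.
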